8 ASSESSMENT OF SAFETY

8.1 Safety Variables

Safety of Albutein 20% will be evaluated in this study.

- The number of suspected ADRs, including ARs, and incidence rate of subjects with suspected ADRs during the treatment period and within 72 hours after Albutein 20% infusion completion (or after Albutein 20% infusion stops) will be considered as the main safety variables. The number and incidence rate of overall AEs and SAEs, as well as deaths and discontinuations due to AEs will be also collected and analyzed.
- Vital signs will be recorded at each scheduled visit and in particular before and after each Albutein 20% administration.
- Clinical laboratory test parameters (blood cell counts, platelet count, INR, fibrinogen, etc.) will be assessed according to the study schedule.
- Physical examinations will be assessed according to the study schedule.
- According to the investigator's assessment, all clinically relevant changes in vital function and laboratory testing parameters findings will be considered AEs.

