9.1.3.1 Adverse Events

Adverse events will be coded and classified using MedDRA[®] terms (system organ class and preferred terms).

When a causal relationship of an AE is classified by the investigator as definitively or possibly related, the event will be defined as a suspected ADR. A suspected ADR with a causal relationship of "definitively related" will be defined as an AR. The sponsor will consider the investigator's causality assessment and also provide its own assessment. If there is any disagreement in the causality assessment between the investigator and the sponsor, a separate summary of suspected ADRs/ARs will be provided.

For summary purpose, AEs will be classified as treatment-emergent AEs (TEAEs) or non-TEAEs depending on the comparison of AE onset date/time with the start date/time of study treatment. A TEAE will be defined as an AE which occurs between the start of study treatment and the final visit of the clinical study. A non-TEAE will be defined as an AE which occurs prior to the start of study treatment. Non-TEAEs and TEAEs will be summarized separately.

In addition, TEAEs, including suspected ADRs, will be summarized by each treatment group, system organ class, preferred term, causal relationship, severity, and seriousness (serious versus non-serious) using descriptive statistics. At each level of summarization, a subject will only be counted once per system organ class or preferred term using the most severe AE or the AE with the strongest causal relationship to the treatment.

AEs temporally associated with the infusion of the IP (ie, infusional AEs, including infusional suspected ADRs) will be summarized by presenting infusion/subject incidences and percentages and listed.

Subjects with SAEs, AEs leading to death, or who withdraw from the study because of an AE will also be individually listed and summarized.

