5.4.2 Safety Variables

The following safety variables will be assessed in this study:

- The number of suspected adverse drug reactions (ADRs; defined as possibly and or definitely drug related), including ARs (defined as definitely drug related), and incidence rate of subjects with suspected ADRs during the treatment period and within 72 hours after Albutein 20% infusion completion (or after Albutein 20% infusion stops) will be considered as the main safety variables. Due to the open label design of this trial, ADRs will be assigned causality to Albutein and ADRs will not be applicable to SMT.
- The number and incidence rate of overall treatment-emergent adverse events (TEAEs) and Serious AEs (SAEs), in addition deaths and discontinuations due to AEs will be also collected and analyzed.
- Clinically significant/relevant changes in vital function and clinical laboratory testing parameters, as determined by the investigator, will be documented as AEs and reported as part of the adverse event summaries.
- Vital signs (temperature, blood pressure, heart rate, respiratory rate) at each scheduled visit and, in particular before and after each Albutein 20% administration.
- Clinical laboratory test parameters including:
- Chemistry (Sodium, potassium, creatinine, blood urea nitrogen (BUN), calcium, magnesium, lactate dehydrogenase (LDH), aspartate aminotransferase (AST), alanine aminotransferase (ALT), gamma-glutamyl transpeptidase (GGT), alkaline phosphatase (ALP), glucose, total bilirubin, direct and indirect bilirubin, C-reactive protein (CRP), serum albumin [pre and post albumin 20% infusion in the SMT + A20% group])
- Hematology (Hemoglobin, hematocrit, platelets, red blood cell count, white blood cell (WBC) count with differential, total neutrophils, lymphocytes, monocytes, eosinophils, basophils)
- Lactate
- Coagulation (International normalized ratio (INR), fibrinogen, prothrombin time)
- Albumin functional capacity assessment (Albumin binding capacity)
- Urine pregnancy test (Qualitative urine β -human chorionic gonadotropin [β -HCG])
- Procalcitonin
- Biomarker (interleukin [IL] 6 (IL-6), IL-8, IL-10) and tumor necrosis factor alpha [$TNF\alpha$])

Number	BIG-CL-SP-000319		
	IG1601	Statistical Analysis Plan	
Effective Date	09-Sep-2024	Status	2.0
Effective	19 of 52		
Page			

- Plasma biomarker retains and transcriptome
- Physical examinations

6 General Statistical Considerations

All analyses will be conducted using SAS Version 9.4 or higher.

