10.1 Adverse Events

Adverse Events are coded using the MedDRA coding dictionary (a version within 1 year of the data base lock). A treatment emergent adverse event (TEAE) is defined in [Section 6.1.6](#). A suspected ADR is an adverse event with causal relationship of "definitely related" or "possibly related", as classified by the investigator. An adverse reaction (AR) is an adverse event with causal relationship of "definitely related", as classified by the investigator.

A temporally associated (i.e., infusional) AE is an AE that is temporally associated with the infusion of Albutein 20%, and is identified as an AE that occurs during an Albutein infusion (as recorded by the investigator), or within 72 hours following an Albutein infusion (determined by calculating the time from infusion end to AE start). These definitions only apply to subjects in the SMT + Albutein 20% group.

All adverse events, both treatment-emergent and non-treatment emergent, will be included in a listing, with a flag to distinguish whether or not the event is treatment-emergent.

An overall summary of TEAEs will present the number of TEAEs, and the number and percentage of subjects with TEAEs, in the following categories:

- AE with Onset Prior to Treatment
- TEAE
- Suspected ADR
- AR
- TEAE Leading to Death
- Serious TEAE
- Serious Suspected ADR
- Serious AR
- Non-Serious TEAE
- TEAE Leading to Drug Interruption
- TEAE Leading to Drug Withdrawal
- TEAE Leading to Study Withdrawal

GRIFOLS	Number	IG1601	Big-CL-SP-000319
	Version	2.0	Statistical Analysis Plan
	Effective	Effective Date	09-Sep-2024
	Page		41 of 52

- Temporally associated TEAEs

In addition, TEAEs will be summarized in the following ways:

- SOC / PT – summary of number of TEAEs and number/percentage of subjects with at least one TEAE by treatment, SOC and preferred term
 - A select subset of TEAE summaries will also include number of events by SOC and preferred term
- PT – summary of number of TEAEs and number/percentage of subjects with at least one TEAE by treatment and preferred term
- SOC/PT/Severity – summary of number of TEAEs and number/percentage of subjects with at least one TEAE by treatment, SOC, preferred term, and severity
- SOC / PT / Causality – summary of number of TEAEs and number/percentage of subjects with at least one TEAE by treatment, SOC, preferred term, and causality

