- PT Rates – summary of number of infusions, number of adverse events, rate of adverse events per infusion, and rate of adverse events per exposure week by preferred term. Rate per infusion is defined as total number of events divided by total number of infusions received. Rate per exposure week is defined as total number of events divided by total duration of exposure in weeks. This summary applies to the SMT + Albutein 20% group only

At each level of summarization, a subject will only be counted once per SOC or preferred term, using the most severe AE or the AE with the strongest causal relationship to the treatment as applicable. Summary tables will be sorted in descending frequency within the SMT + Albutein 20% group, then descending frequency with the SMT group, and then alphabetically.

The following table identifies the sets of adverse events that will be presented for each of these types of summaries.

Adverse Event Subset	TEAE Summary					Listing
	SOC / PT	PT	SOC / PT / Severity	SOC / PT / Causality	PT Rates*	
AE with Onset Prior to Treatment						
TEAEs						
Suspected ADR						
AR						
TE SAEs						
Non-serious TEAEs	 #					
TEAEs leading to Study Withdrawal						
TEAEs leading to Death						
Temporally associated TEAEs*						

* This subset applies only to the SMT + Albutein 20% group.

This summary will include number of events by SOC / PT.

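### SAP 10.1 tables suspected ADRs and 72-hour infusion events separately but never their overlap, and leaves out the protocol's infusion percentages and causality-disagreement summary without declaring the changes

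*SAP*

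**What the plan says.** Protocol 8.1 names among the main safety variables the number of suspected ADRs and the "incidence rate of subjects with suspected ADRs during the treatment period and within 72 hours after Albutein 20% infusion completion". SAP 5.4.2 repeats this, ending "infusion completion (or after Albutein 20% infusion stops) will be considered as the main safety variables".

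Protocol 9.1.3.1 then says what is to be shown. Events temporally associated with infusion, that is "infusional AEs, including infusional suspected ADRs) will be summarized by presenting infusion/subject incidences and percentages and listed". On causality: "If there is any disagreement in the causality assessment between the investigator and the sponsor, a separate summary of suspected ADRs/ARs will be provided".

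SAP 10.1 works with two separate sets.

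- A suspected ADR is an AE judged possibly or definitely related, "as classified by the investigator", with no 72-hour limit.
- A temporally associated AE starts during an infusion or within 72 hours of its end, with no causality limit.

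Both are categories in the overview, which gives events and number and percentage of subjects. Both are rows in the table introduced by "The following table identifies the sets of adverse events that will be presented for each of these types of summaries". The per-infusion measure is in the preferred-term rates: "Rate per infusion is defined as total number of events divided by total number of infusions received".

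**The concern.** The SAP names the 72-hour window when it defines its main safety variable, then applies that window only to events of any causality. The protocol asks in terms for the suspected ADRs inside the window, and nothing planned in SAP 10.1 produces them. Two further protocol commitments go the same way: the percentage of infusions with an event, and the second summary when the sponsor's causality call differs from the investigator's.

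Protocol 2.3 lists anaphylactic shock, heart failure and pulmonary edema as the most serious reactions and anaphylactoid reactions as the most common, so events close to infusion and judged related are a natural first place for a safety reader to look. The trial is open-label, and SAP 5.4.2 states that ADRs do not apply to the SMT arm. There is therefore no control-arm ADR figure to set against the Albutein figure, and the sponsor's assessment is the protocol's own cross-check on the investigator's. Under SAP 2, a table not identified in the plan and produced later would be documented in the study report as post hoc or unplanned.

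**Working it through.** This is mainly a comparison of text; no sample size, power or alpha figure is involved.

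**Step 1. Protocol 9.1.3.1 against SAP 10.1.**

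| Protocol commitment | SAP 10.1 |
|---|---|
| Infusional AEs by subject, n and % | Kept (overview category) |
| Infusional AEs by infusion, n and % | Not planned; events per infusion by preferred term instead |
| Infusional suspected ADRs, by infusion and by subject | No overview category, no row |
| Infusional AEs listed | Kept in the listing of all AEs; the only flag specified is treatment-emergent status |
| Separate ADR/AR summary on disagreement | Not planned |

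This reading uses row and category names only. It does not depend on which cells of the table are ticked.

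**Step 2. Can the overlap be recovered from the two planned totals?** Let E be all TEAEs in the Albutein arm, A the suspected ADRs and T the temporally associated TEAEs. The number in both sets can lie anywhere from max(0, A + T − E) to min(A, T). The planned tables give A, T and E, so they bound the overlap but do not determine it. The two sets would coincide by construction only if the window filled the dosing interval, and it does not:

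- 10-day interval: 3/10 = 30%
- 8-day interval: 3/8 = 37.5%
- 12-day interval: 3/12 = 25%

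**Step 3. Is the infusion denominator well defined?** Infusions fall on Days 1, 11, ..., 361, so the count is (361 − 1)/10 + 1 = 37. This reproduces the 37 expected infusions for completers in SAP 8.4.

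**Step 4. Does events per infusion replace the percentage of infusions affected?** The SAP measure is events / infusions. The protocol measure is infusions with at least one event / infusions. With assumed counts of 10 events over 100 infusions, the first is always 10/100 = 0.10. The second depends on where the events fall:

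- in 10 infusions: 10/100 = 10%
- in 5 infusions: 5/100 = 5%
- in 2 infusions: 2/100 = 2%

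The SAP gives its rate by preferred term. Within one term the two measures agree if the term occurs at most once per infusion. Across terms, one infusion can contribute to several rows, so the rows cannot be added to give the infusions affected by any event.

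**Step 5. Are the changes declared?** SAP 12 covers the CLIF-C AD criterion, country and European region, time to randomization, the TEAE definition, longitudinal outcomes and ethnicity. It explains one adverse event departure, the TEAE definition, but none of the three items above.

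**The case against.** The strongest reply is that the main safety variable is in fact delivered. It can be read as the treatment period plus a 72-hour tail. SAP 6.1.6 sets no upper limit on TEAEs after the first dose, so the whole-period suspected ADR summary, with events and subject percentages, covers that reading. This stands. A reader might infer that the main safety variable is not produced at all, and the documents do not support that. What the reply does not answer is Protocol 9.1.3.1, which names infusional suspected ADRs separately.

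Second, all AEs are listed and per-infusion rates are kept. Both are true. Infusional AEs are not unlisted, and per-infusion reporting is changed, not abandoned. Only the percentage of infusions affected is missing.

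Third, the protocol also defines a suspected ADR by the investigator's classification, and its second summary is conditional on disagreement. So the SAP definition is consistent with the protocol, and silence is not revocation. Still, the sponsor must make its own assessment under Protocol 8.3.4, and the SAP has no provision for the case in which the two differ.

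Fourth, safety is descriptive, with no hypothesis test, and the overlap can be derived from collected onset times, infusion times and causality. That limits the consequence but does not pre-specify the table.

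**Conclusion.** The plan should be corrected. Three protocol-stated safety summaries are missing from SAP 10.1 and undeclared in SAP 12: suspected ADRs during or within 72 hours after an infusion, the percentage of infusions affected, and the separate summary on causality disagreement. The matter is one of protocol and SAP alignment for descriptive safety; no error rate or efficacy conclusion changes.

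The documents allow no estimate of how many ADRs are involved. A reader might treat the share of time outside the window as the share of suspected ADRs outside it. That does not follow, because Protocol 8.3.4 makes a plausible temporal sequence one of the causality criteria, so related events need not be spread evenly between infusions. A reader might also infer that the SAP rate inflates the protocol's percentage by the number of coded terms per infusion. It does not, because rates are by preferred term and three different terms in one infusion add one event to each of three rows.

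The conclusion assumes that the protocol's infusion/subject wording means both by infusion and by subject.

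**What to change.** In SAP 10.1:

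- Add a temporally associated suspected ADR category to the overview and a matching row to the AE-set table, with events, subjects n and %, and infusions with at least one such event n and %.
- Give infusions with at least one event, n and %, for temporally associated TEAEs as well, next to the event rates already planned.
- Add a 72-hour flag to the existing AE listing.
- Restore the separate suspected ADR/AR summary by the sponsor's assessment, produced when the two assessments differ, as the protocol states.

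If any of these is left out on purpose, say so and why in SAP 12.

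The cost is SAP wording and a few tables. The window and the investigator's causality come from data already planned. The sponsor's causality may have to be merged in from another source, because the AE eCRF variables in Protocol 8.3.8 include only one causality item. Conduct, sample size and efficacy analyses are unaffected.

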10.2 Clinical Laboratory Evaluations

Clinical laboratory samples will be analyzed by a central laboratory; the table below lists the planned tests for each panel. All lab tests including unplanned ones with available data will be included in the laboratory listings and summaries.

Test Panel	Planned tests
Hematology	Hemoglobin, hematocrit, platelets, red blood cell count, WBC count with differential
Chemistry	Sodium, potassium, creatinine, BUN, calcium, magnesium, LDH, AST, ALT, GGT, ALP, glucose, total bilirubin, direct and indirect bilirubin, CRP, lactate, serum albumin
Coagulation	International normalized ratio (INR), fibrinogen, prothrombin time
Albumin functional capacity assessment	Albumin binding capacity
Systemic inflammation assessment	Procalcitonin, WBC (hematology panel), CRP (chemistry panel)

Laboratory parameters will be presented in alphabetical order within test panel; the differential of WBC counts will be presented alphabetically following the WBC results.

All results and normal ranges will be displayed in SI units. All data will be listed for each subject. Values outside of normal range will be flagged.

Summary tables for all continuous/quantitative laboratory parameters (including hematology, chemistry, coagulation and systemic inflammation assessment) will present descriptive statistics for original values and change from baseline by treatment and visit. For summarization, concentration values that are reported as “<X.XX” the concentration will be imputed using the X.XX value multiplied by a factor of 0.9. For concentration values that are reported as “>X.XX” the concentration will be imputed by using the X.XX value multiplied by a factor of 1.1.

For example:

Standard lab result =<0.2 then analysis result=0.2*0.9

Standard lab result =>0.2 then analysis result=0.2*1.1

The above imputation for laboratory values does not apply to the central laboratory values used for all the exploratory endpoint scores. For these exploratory endpoint scores the original result collected will be used with no imputation applied. Shifts from baseline

Number	BIG-CL-SP-000319
IG1601 Statistical Analysis Plan	
GRIFOLS	Bioscience Industrial Group

(with categories L/N/H for low/normal/high) will be presented by parameter, visit and treatment.

Laboratory results that are outside of the normal range will be evaluated by the investigator, and if determined to be clinically significant, will be reported as an adverse event. Clinical significance will not be reported in the laboratory listings or summaries.

Pregnancy tests will be listed for each subject.

Biomarker retentions will be drawn for potential analysis of cytokines (interleukin [IL] 6 (IL-6), IL-8, IL-10, and tumor necrosis factor alpha [TNF α]) and other candidate biomarkers found in the blood which may correlate with disease activity.

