In addition, long-term human albumin administration may also modulate the deleterious effects of inflammatory mediators on mitochondrial and cell function and on organ microcirculation, thus protecting target organs against tissue damage and microcirculatory disturbances. These effects could potentially reduce the incidence of decompensation episodes (ie, ascites, renal or liver failure, hepatic encephalopathy (HE), severe sepsis, septic shock, and acute-on-chronic liver failure [ACLF]) and increase survival rates (21).

Albutein is made from pooled human plasma. Based on effective donor screening and product manufacturing processes, it carries an extremely remote risk for transmission of viral diseases, including a theoretical risk for transmission of Creutzfeldt-Jakob disease (CJD). Although no cases of transmission of viral diseases or CJD have ever been identified for albumin, the risk of infectious agents cannot be totally eliminated (1).

Albutein is contraindicated in patients with severe anemia or cardiac failure in the presence of normal or increased intravascular volume. The use of Albutein is contraindicated in patients with a history of allergic reactions to this product. The most serious adverse reactions (ARs) are anaphylactic shock, heart failure, and pulmonary edema. The most common ARs are anaphylactoid type reactions. For additional information on potential risks and adverse events (AEs), please also refer to the IB (1) and any additional data supplied by the sponsor.

2.4 Description of and Justification for the Route of Administration, Dosage, Dosage Regimen, and Treatment Periods

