8.2.3 Clinical Laboratory Evaluations

Considering the medical history inherent in subjects with decompensated cirrhosis, certain laboratory abnormalities, while clinically significant, will be expected in this medical context, and would not indicate treatment-emergent worsening or a new AE (being instead an extension of medical history/underlying pre-existing conditions). Examples include: low platelet count, decreased albumin, prolonged prothrombin time/INR, elevated bilirubin, and abnormal transaminases. These conditions would be expected laboratory consequences of cirrhosis/decompensated liver diseases. These results would not be considered individual AEs as they most likely reflect manifestations of existing cirrhosis and hepatic decompensation, unless abnormalities worsen after initiation of study treatment and become accentuated to a medically significant degree in a treatment-emergent fashion.

Central clinical laboratory data for renal, hepatic, and hematological parameters will be listed for each clinical study subjects.

The investigator will be required to classify laboratory results out of the normal range reported by the central laboratory as clinically significant or not according to his/her criteria.

Laboratory results out of the normal range judged by the investigator as clinically significant will be considered AEs.

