Unless otherwise noted, for continuous variables, descriptive statistics for continuous/quantitative data will include the number of non-missing values, mean, standard deviation, median, 25th percentile (Q1), 75th percentile (Q3), minimum and maximum. In general, the mean, median, Q1 and Q3 will be presented to one decimal place greater than the original data, standard deviation will be 2 decimal places greater than the original data, and the minimum and maximum will have the same number of decimal places as the original data. For categorical/qualitative data, descriptive statistics will include counts and percentages (rounded to 1 decimal place) per category.

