6.1.5 Visit Windows

For safety analyses (laboratory and vital signs data) and efficacy analyses, by-visit summaries and analyses will analyze assessments by visit as designated on the CRF; visit remapping based on study day to an analysis visit window won't be applied. Unscheduled visits will be excluded from by-visit summaries and analyses. The Early Discontinuation

GRIFOLS	Bioscience Industrial Group	Number	IG1601	Version	2.0	Status	Effective	Effective Date	09-Sep-2024	Page	20 of 52
		IG1601	Statistical Analysis Plan								

visit will be summarized as a separate visit, without adjusting for the timing of assessments for subjects that discontinue early.

For the analyses of exploratory endpoints, the early discontinuation visit will be mapped to an assessment visit. The mapping will be based on the timing of a subject's assessment visit, relative to their Study Day 1. A detailed list of the parameters and the mapping rules to be applied is provided in [Appendix 4](#).

For cases where multiple assessments are recorded for a parameter within a single visit window, the following rules will be applied for each parameter:

- If 2 or more assessments are mapped to the same visit window, then the non-missing assessment closest to the scheduled visit target day will be used in the analysis.
- If 2 assessments are equidistant from the visit target day, the later non-missing observation will be used in the analysis.

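### For laboratory tests already abnormal at entry, the low/normal/high shift tables cannot show further worsening in the same direction, and no baseline-to-worst table counts it

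*SAP*

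**What the plan says.** SAP 10.2 (Clinical Laboratory Evaluations) plans two summaries. Tables for the quantitative parameters "will present descriptive statistics for original values and change from baseline by treatment and visit". Shifts from baseline "with categories L/N/H for low/normal/high) will be presented by parameter, visit and treatment". SAP Section 6 (General Statistical Considerations) defines the descriptive statistics as the number of non-missing values together with "mean, standard deviation, median, 25th percentile (Q1), 75th percentile (Q3), minimum and maximum".

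SAP 6.1.5 (Visit Windows) covers laboratory and vital-sign data: "Unscheduled visits will be excluded from by-visit summaries and analyses". It keeps the early discontinuation visit in the safety tables as a separate visit, without regard to when it took place.

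SAP 10.2 also says: "All lab tests including unplanned ones with available data will be included in the laboratory listings and summaries". On listings it says: "All data will be listed for each subject. Values outside of normal range will be flagged". Clinical significance is kept out of the laboratory outputs; a result that the investigator judges clinically significant is reported as an adverse event.

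Protocol 8.2.3 explains that certain laboratory abnormalities are expected in decompensated cirrhosis and would not by themselves be new adverse events: "Examples include: low platelet count, decreased albumin, prolonged prothrombin time/INR, elevated bilirubin, and abnormal transaminases". The exception is worsening after the start of treatment that reaches a medically significant degree.

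**The concern.** A three-category shift table is informative when subjects start in the normal category. For a test that is typically abnormal in this disease, a subject who begins high and rises further is recorded as high-to-high, and one who begins low and falls further as low-to-low. The shift table is the only categorical display in the laboratory section. SAP 10.2 plans no severity grades, no multiples of baseline or of a normal limit, and no worst post-baseline value per subject.

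This matters because the trial is open-label (Protocol 4.3.3) and Protocol 9.1.3 rests the safety comparison on review of descriptive statistics. SAP 5.4.2 makes adverse drug reactions inapplicable to the control arm, so central-laboratory values are one of the main objective comparisons between arms. Hemoglobin deserves a count by arm for a reason in the protocol itself: "Albutein is contraindicated in patients with severe anemia or cardiac failure in the presence of normal or increased intravascular volume" (Protocol 2.3). An excess of subjects in one arm with marked falls in platelets or hemoglobin, or marked rises in transaminases, could pass without any table stating how many there were.

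**Working it through.** The plan gives no figure on this point to reproduce. The check sets the displays side by side and then sizes the loss.

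**1. What each laboratory display can show.**
- *Shift table:* normal-to-low and normal-to-high remain visible. Same-direction worsening from an abnormal baseline does not. Because the table is by visit, it also gives no count of subjects who ever shifted.
- *By-visit statistics:* change from baseline is tabulated, so worsening within a category does enter. The minimum and maximum show one extreme value per visit. The quartiles respond only partly: if 10% of an arm moves to the far end, the upper quartile moves to the 1 − 0.15/0.90 = 0.83 point of the other subjects' distribution, however large the worsening. Neither is a count of subjects.
- *Listings:* every value appears, flagged if out of range, but without comparison by arm.

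**2. What other sections add** (SAP 9.3.1 to 9.3.5, 9.3.8 and 9.3.9; cut-points in Protocol Appendix 3).

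| Test | Named in Protocol 8.2.3 | Other display by arm |
|---|---|---|
| Bilirubin | yes | CLIF-C OF sub-score (6, 12 mg/dL), Child-Pugh sub-score, MELD |
| INR | yes | CLIF-C OF sub-score (2.0, 2.5), Child-Pugh sub-score, MELD, CLIF-C AD |
| Albumin | yes | Child-Pugh sub-score, own exploratory analysis |
| Creatinine | no | CLIF-C OF sub-score (2, 3.5 mg/dL), MELD, CLIF-C AD; HRS counts |
| Sodium | no | component of CLIF-C AD; hyponatremia counts |
| Platelets | yes | none |
| Transaminases | yes | none |
| Hemoglobin | no | none graded (GI bleeding is counted as an event) |

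The scores are displayed by visit. The complications are counted per subject, but as events that the investigator reports. ACLF is counted cumulatively through Months 3, 6 and 12, but it is a composite and isolates no single test. None gives a subject's worst value for a given test against baseline.

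**3. Size of the loss.** Let *b* be the share of an arm already out of range in the direction of worsening, and *w* the share that truly worsens. If worsening is independent of baseline category, the shift table can show at most *w* × (1 − *b*), so the proportion of worsening subjects missed is at least *b*. Take *w* = 10% of 205 per arm (SAP 6.2), which is 20.5 subjects:

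| *b* (assumed) | Visible share, 0.10 × (1 − *b*) | Visible subjects, × 205 |
|---|---|---|
| 0.1 | 9% | 18.5 |
| 0.3 | 7% | 14.4 |
| 0.5 | 5% | 10.3 |
| 0.7 | 3% | 6.2 |
| 0.9 | 1% | 2.1 |

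Both *b* and *w* are assumptions. The loss is total only at *b* = 1.

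**4. Transient changes.** From Day 31 the laboratory visits are 30 days apart, so an abnormality lasting 10 days (assumed) with random onset meets a scheduled draw with probability 10/30 = 0.33. Detection is better earlier, when visits fall on Days 1, 11 and 31. Any unscheduled draw in between stays out of the by-visit tables.

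**5. Balance of scheduled draws.** The albumin arm has extra infusion visits (Days 21, 41, 51 and so on), but Protocol 7.2.1.2.3 and Appendix 1 schedule no laboratory panel then. Both arms have the same post-baseline panel schedule: Day 11 and Months 1 to 12, or 13 visits. The exception is the post-infusion serum albumin sample in the albumin arm. Vital signs differ: they are measured at every infusion visit, before and after the infusion.

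**The case against.** The strongest reply is that the plan already compares much of this. Bilirubin, creatinine, INR and sodium enter scores analyzed by arm, and the CLIF-C OF bands separate severity inside the high category. For these exploratory endpoints the early discontinuation visit is mapped into the analysis visits. Hyponatremia, HRS and GI bleeding are counted by arm without restriction to scheduled visits. This stands, and it narrows the gap to hemoglobin, platelets and transaminases, plus a missing per-subject worst value for the others.

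Some stronger readings are tempting, and the documents do not support them:
- A reader might infer that the protocol expects most subjects to be out of range. Protocol 8.2.3 gives examples and no proportion, and hemoglobin, creatinine and sodium are not among them.
- A reader might infer that worsening cannot appear in the shift tables at all. Subjects who start normal can still shift.
- A reader might infer that only means are tabulated. SAP Section 6 adds the median, quartiles, minimum and maximum.
- A reader might infer that these tables are the only comparison free of attribution. Treatment-emergent events, deaths and serious events (SAP 10.1) and vital signs (SAP 10.3) are also tabulated by arm regardless of causality.

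It can also be said that the documents do not state why unscheduled draws are taken, and that Protocol Table 7-1 sends all testing after screening to a central laboratory, so acute local results may never reach the dataset. Both points stand and limit what a version with unscheduled results can recover. The worry that a worst-value table would favor detection in one arm applies to unscheduled draws. For the panel tests it does not apply to the common visit schedule, although unequal follow-up would remain.

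**Conclusion.** The point holds as a cheap improvement. For tests abnormal at baseline, the shift tables of SAP 10.2 hide further worsening in the same direction, and no table counts subjects per arm by worst value. The gap is fullest for hemoglobin, platelets and transaminases, and partial for bilirubin, creatinine, INR and sodium. For hemoglobin, the hiding depends on how many subjects start low, which the documents do not say; the absence of any graded or worst-value display does not depend on that.

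The size is conditional. At least a share *b* of worsening subjects is missed in the shift table, where *b* is the unknown baseline out-of-range share and worsening is assumed independent of baseline category. No efficacy test, sample size or error rate is affected.

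**What to change.** In SAP 10.2, add by arm a table from baseline to worst post-baseline value, in steps relative to baseline or to the normal limit that are fixed before the tables are run. Cover at least hemoglobin, platelets, transaminases, creatinine, sodium, INR and bilirubin.

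- *Main version:* the laboratory visits scheduled in both arms, plus early discontinuation.
- *Second version:* the same, with unscheduled results added.
- *Wording:* state whether *unplanned* tests in SAP 10.2 means unplanned analytes, which the context of the planned-test table suggests, or unscheduled draws. Reconcile this with the exclusion in SAP 6.1.5.
- *Unchanged:* the by-visit tables stay.
- *Vital signs (SAP 10.3):* do not add a worst-value table unless it is restricted to visits common to both arms, because the albumin arm has extra infusion-day measurements.

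The cost is SAP wording and one extra table per panel and version, from data already collected. The downside is possible detection bias from unequal unscheduled draws or follow-up; the scheduled-only version limits this.
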